# Subject Disposition

Subject disposition, including the total number of participant's enrolled, randomized, completed, early terminations and withdrawals, will be presented. In addition, a listing will be provided with the reasons for discontinuation.

#### Demographics and Baseline Characteristics

Standard subject demographics (e.g., age and gender) and baseline characteristics will be summarized for all participants enrolled and for evaluable subjects.

#### Treatment Compliance

It is expected that the drop-out rate will be low as the study is of short duration and will be completed in a controlled, in-lab setting. Any discontinued participants or protocol deviations will be documented.

#### **Primary Efficacy Analysis**

The primary efficacy measure for this study will be the cumulative or average slow-wave activity (SWA), which will be measured at multiple EEG electrode locations (channels). As stated in the study procedures, two PSG nights will be collected for each therapy.

The primary SWA endpoint will be the average of the two nights, but secondary analyses will include separate assessments of the first and second nights within each therapy. The data will be evaluated to determine whether they meet the assumptions of parametric methods. SWA will be compared between the Active and Sham conditions, using either a paired t-test or the nonparametric Wilcoxon Signed Ranks test, depending on the distribution of the paired differences. The comparisons will be performed within and between EEG channels. The significance level will be a two-sided alpha of 0.05, and if necessary, this will be adjusted for multiple comparisons.

RESPIRONICS

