# C. Study Procedures and Measurements:

Participants may be pre-screened over the phone by the site or a market research firm to determine eligibility. A screening script will include a general review of key inclusion and exclusion criteria, the STOP-BANG questionnaire to assess the risk / possibility of an undiagnosed sleep disorder [46] and other questionnaires. Participants that meet all eligibility criteria will be asked to come into the office for a screening daytime visit (Visit 1) involving a detailed presentation of the study (informed consent) and an interview to verify eligibility and work schedules.

Participants who are interested and eligible will be consented. Participants will scheduled for a second daytime visit, 5 overnight lab visits, and provided with information on use of the actigraph. At Daytime Visit 2, participant qualification will be assessed based on the PowerSleep device data, actigraphy, and sleep logs. Qualifying participants will be randomized and scheduled for their sleep lab visits.

Participants will use the PowerSleep device within the active and sham study arm for two nights each week. After completing a baseline night in the lab, participants will sleep in the sleep lab two consecutive nights for two consecutive weeks. The first week participants will be randomized to active or sham and complete two consecutive nights. Participants will be asked to come in the same nights the following week to cross-over to the other arm of the study.

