# Actigraphy review:

The sleep log and actigraph data will be reviewed by trained study staff prior to randomization to ensure participants continued eligibility.

Eligible participants will be randomly assigned to active or sham treatment during this visit in a 1:1 ratio. Participants and study staff will be blinded to the treatment they are receiving during each work week.

*Active treatment*: Participants will wear the PowerSleep device with soft audio tones (below 65dB to prevent arousals from sleep) administered via the speakers during deep sleep throughout the night.

*Sham treatment:* Participants wear the same PowerSleep device as with the active treatment, however no audio tones will be administered via the speakers.

Those participants that state they have heard tones during the baseline night will be set to a sensitive setting.

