# **Determination of Sample Size**

100 participants may be screened, up to 75 participants will be enrolled (randomized) in order to ensure at least 50 complete data sets. An interim analysis (N=9) from an international study of similar design suggests that between 24-47 participants would be required to reach statistical significance for the primary endpoint of slow-wave activity (SWA).

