#### Secondary Efficacy Analysis

The daytime outcomes will be analyzed using the same statistical model as the SWA data.

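### The planned paired test ignores the randomised order of the crossover; modelling period and sequence is a cheap improvement that preserves power if week 2 differs from week 1

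*Combined protocol and SAP*

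**What the plan says.** Section III.C (Study Procedures and Measurements) describes a two-period crossover. "The first week participants will be randomized to active or sham and complete two consecutive nights", and then: "Participants will be asked to come in the same nights the following week to cross-over to the other arm of the study". The Actigraphy review subsection gives the allocation: "Eligible participants will be randomly assigned to active or sham treatment during this visit in a 1:1 ratio". It does not say whether order is blocked.

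Under Primary Efficacy Analysis, "The primary SWA endpoint will be the average of the two nights", and "SWA will be compared between the Active and Sham conditions, using either a paired t-test or the nonparametric Wilcoxon Signed Ranks test", the choice depending on how the paired differences are distributed. The level is two-sided 0.05. Secondary Efficacy Analysis adds: "The daytime outcomes will be analyzed using the same statistical model as the SWA data".

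No section includes a period or sequence term. Order appears in the statistical section only under General Considerations, where participants whose order was switched are analysed both as randomised and as treated. That section also limits the primary analysis to completers with at least one usable night per condition, so the two orders can end up unequal.

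**The concern.** In a two-period crossover, anything that differs between week 1 and week 2 enters each participant's active-minus-sham difference. The sign is plus for those who had active in week 2 and minus for those who had it in week 1. A test on the pooled differences treats this systematic pattern as noise. If the two orders are unequal, part of the pattern is counted as treatment effect. The randomised order is known for everyone, so the information needed to remove the shift is already collected.

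At stake are some power and interval width on slow-wave activity (SWA). The daytime outcomes have the same exposure, and a learning or familiarity shift is more plausible there because the tests are repeated in week 2.

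**Working it through.** **Inputs.** From the documents: 1:1 order; two-sided 5%; "up to 75 participants will be enrolled (randomized) in order to ensure at least 50 complete data sets"; and an interim analysis of nine participants from another study that "suggests that between 24-47 participants would be required to reach statistical significance". Not given: the SD of the paired difference, the power behind 24-47, and any week-2 minus week-1 shift. The shift is therefore varied, in units of the SD of the paired difference within an order.

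**The plan's own figure.** 24-47 cannot be reproduced without an effect size and power. Assuming 80% power and a paired t-test, the noncentral t gives standardised effects d = 0.597 (N=24) and d = 0.417 (N=47). For reference, d = 0.404 gives 80% at N=50 and lies just below that range.

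**Model.** D = d + s × shift + e, with e ~ N(0,1), s = +1 if active is in week 2 and −1 if it is in week 1.

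*Equal orders.* The shift cancels in the mean of D, whose sampling SD is 1/√50 = 0.141 with or without order in the model. The estimated variance of D, however, is inflated by about 1 + shift² (exactly, shift² × 50/49 is added):
- 0.25 SD: 1 + 0.0625 × 50/49 = 1.064, so the standard error is 3% too large.
- 0.5 SD: 1 + 0.25 × 50/49 = 1.255, so it is 12% too large.

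Type I error of the paired t falls to about 4.4% and 2.9%.

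*Unequal orders.* The estimate moves by shift × (n with active in week 2 − n with active in week 1)/N. At 30/20 and 0.5 SD this is 0.5 × 10/50 = 0.10 SD, up or down.

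**Power by simulation.** The comparison is a one-sample t on D against the average of the two sequence means, with pooled variance and N−2 degrees of freedom.

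| N (split) | d | Paired t, 0.25 SD | Paired t, 0.5 SD | Order modelled |
|---|---|---|---|---|
| 50 (25/25) | 0.417 | 81% | 76% | 82-83% |
| 50 (25/25) | 0.597 | 98% | 97% | 99% |
| 50 (25/25) | 0.404 | 78% | 73% | 80% |
| 75 (38/37) | 0.417 | 94% | 90-92% | about 95% |

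The range at N=75 depends on which order is larger. The rank tests behave alike: at N=50, 25/25, d = 0.417, signed-rank power is 79% and 73%, against 80% for the rank-sum test on week differences.

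**Unequal splits, N=50, d = 0.404.**
- 28/22, 0.25 SD: paired-t power is 84% or 72% depending on which order is larger, against 79% with order modelled. Type I error is about 4.9%, so not inflated.
- 30/20, 0.5 SD: power is 90% or 47%, against 78%. Type I error is about 7% (about 5.6% at 0.25 SD).

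**Chance of such splits among 50 analysed.**

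| Allocation | 28/22 or worse | 30/20 or worse |
|---|---|---|
| Simple 1:1 | 48% | 20% |
| Balanced 75, 25 lost at random | 23% | 2.9% |
| Balanced 60, 10 lost at random | 8% | 0.1% |

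**Break-even.** Averaged over allocation at d = 0.404, N=50, the two analyses have equal power at a shift of about 0.15 SD (simple allocation) or 0.10 SD (balanced). Below that, modelling order gains nothing.

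**The case against.** The strongest reply is that the planned test is valid and the documents show no shift. If loss is unrelated to order, the paired t-test is unbiased and holds about 5% averaged over simple 1:1 allocation; with balanced orders it is conservative. For SWA the design already works against a shift: there is a baseline laboratory night with the device and electrodes, the same nights are used each week, bed and wake times are habitual, and two nights are averaged. For the daytime tests there is a practice session before the first study night, and the word-pair retention score subtracts same-evening recall, so a general practice gain tends to cancel. Fifty is also the floor for complete data sets; with more participants or a larger effect the loss shrinks to a point or two. Treatment Compliance expects low drop-out, which makes losing 25 of 75 unlikely.

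All of this stands, and it sets the weight of the point. It does not favour the planned test, because the analysis must be fixed before the shift is known and the premium for modelling order is small. The practice session is described only before week 1, and reaction-time and verbal-fluency testing recur in week 2, so a shift there remains plausible.

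A reader might go further and infer that the primary test is biased or has inflated type I error. The documents do not support that. Inflation needs a marked split and a shift together: it appears at 30/20 but not at 28/22. Nor does a shift with equal orders make the estimate itself less precise. Only its reported standard error is too large.

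**Conclusion.** The point holds as a cheap improvement. The plan leaves randomised order out of the analysis of a randomised-order crossover, and including it is better or no worse unless the shift is very small. At N=50 with equal orders, the loss avoided is about 1 to 2 points of power at a 0.25 SD shift. At 0.5 SD it is about 6 to 7 points if d is near 0.417 and 1 to 2 points if d is near 0.597. With unequal orders, modelling also stops the estimate from moving with the shift.

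These sizes rest on assumptions: that 24-47 meant 80% power, that differences are roughly normal, that loss is unrelated to order, and that a shift of the illustrated size exists. A reader might infer that the trial is underpowered as planned; no shift or SD is documented, so that does not follow.

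**What to change.** Keep the two-night average as the primary endpoint. Under Primary Efficacy Analysis, replace the sentence naming the tests with:

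> Active and Sham will be compared on SWA (two-night average; in secondary analyses, each night separately) in a model with fixed effects for treatment, period and sequence and a random participant effect. This is equivalent to a two-sample t-test of week-2 minus week-1 differences between the two sequence groups, the treatment effect being half the difference in means. If the distribution of these differences within sequence groups does not support parametric methods, the Wilcoxon rank-sum test comparing them between sequence groups will be used instead. For participants whose order was switched, sequence and treatment labels follow the randomised order in the as-randomised analysis and the received order in the as-treated analysis. The number analysed per sequence will be reported. The paired t-test or signed-rank test will be a sensitivity analysis.

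Apply the same analysis to the daytime outcomes under Secondary Efficacy Analysis. The period term does not remove carry-over, and the text should not imply that it does.

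The cost is wording and one degree of freedom (48 instead of 49 at N=50), with no new data or participants. If there is no shift, the power given up at N=50, d = 0.404 is under 0.1 point at 25/25, 0.6 at 28/22, 1.7 at 30/20 and 3.3 at 32/18. At d = 0.597 it is at most 0.7 point over the same splits.

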#### Secondary Efficacy Analysis

The daytime outcomes will be analyzed using the same statistical model as the SWA data.

# Safety Analysis

Safety evaluations will be performed by recording clinical adverse events at the time originally reported and at each visit thereafter. Adverse events will be provided in data listings.

A complete medical history will be obtained at screening, and subjects having any of the outlined exclusion criteria will be immediately discontinued.

# Interim Analysis

An interim analysis is planned when approximately 50% of the enrolled population completes the study. If the effect size observed at the interim is less than originally expected, the sample size may be increased.

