#### B. Study Participants:

It is anticipated that the study will screen 100 individuals in order to complete a total of up to 75 participants. We will recruit male and female participants who satisfy the inclusion and exclusion criteria outlined in the following sections.

Potential participants will be recruited predominantly through media advertisements (ex. local newspapers, flyers), institutional postings, market research firms, word of mouth,

<sup>2 Internal Philips Interim Report- Data on File

or existing site databases of individuals who may have previously indicated an interest in participating in research.

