#### **General Considerations**

The primary analysis will include all completed participants who contributed at least one night of usable PSG data for each therapy condition. If there are participants whose therapy order is switched from their randomized assignment, then the results will be analyzed according to both the as-randomized and the as-treated assignments. If the sleep data are not usable for both nights in a given therapy, those participants will be excluded from the primary analysis, and site(s) may over-enroll to compensate for these missing data. The safety analysis will include all randomized subjects.

All variables will be summarized by descriptive statistics. The statistics for continuous variables include mean, median, standard deviation, minimum, maximum, 95% confidence interval (CI) for the mean, and number of observations. For categorical variables, frequencies and percentages will be presented. All analyses will be conducted using either SAS® or SPSS® software.

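### A low interim effect may raise the sample size while the ordinary paired test at two-sided 0.05 is kept, so the 5% type I error rate is not guaranteed (about 5.0-5.7% under plausible rules)

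*Combined protocol and SAP*

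**What the plan says.** The Interim Analysis section sets the timing, "An interim analysis is planned when approximately 50% of the enrolled population completes the study", and then the adaptation: "If the effect size observed at the interim is less than originally expected, the sample size may be increased". It gives no numerical expectation, formula, ceiling or minimum interim result.

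The final test, in Primary Efficacy Analysis, compares Active with Sham "using either a paired t-test or the nonparametric Wilcoxon Signed Ranks test, depending on the distribution of the paired differences". On the level it says: "The significance level will be a two-sided alpha of 0.05, and if necessary, this will be adjusted for multiple comparisons". Nothing there or elsewhere adjusts for a sample size that depends on the data.

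The planned size can be read in more than one way. Section III.B plans to "screen 100 individuals in order to complete a total of up to 75 participants". Determination of Sample Size says "up to 75 participants will be enrolled (randomized) in order to ensure at least 50 complete data sets", and a small interim from another study "suggests that between 24-47 participants would be required to reach statistical significance". General Considerations adds that "site(s) may over-enroll to compensate for these missing data". It is not clear whether an increase after the interim may go past 75.

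**The concern.** Re-estimating N from a blinded variance barely affects the type I error. Re-estimating it from the observed treatment effect can affect it, and the direction depends on when N is raised. Raising N after a promising interim does no harm to the ordinary test. Raising it after a poor one gives a null treatment more chance to cross 1.96 than the planned N would have given. The plan points the trigger at low results and does not restrict it to promising ones.

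At stake is the meaning of the nominal 5% for the primary slow-wave activity comparison. Under the two kinds of rule computed below, the excess falls on false claims in favour of Active. This point concerns only the sample-size increase. The open choices of endpoint, EEG channel and test are separate matters.

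**Working it through.** **Inputs from the plan.** Two-sided 0.05; paired differences; interim at about 50%; 50 complete sets or 75 enrolled; 24-47 participants required. The interim is therefore taken at 25 of 50 or 37 of 75.

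**Assumptions.** The 24-47 range cannot be reproduced, because no effect size, SD or power is given. Solving backwards with a paired t-test at an assumed 80% power gives a standardised effect of d = 0.597 for 24 participants and d = 0.417 for 47. These serve as the expected effect. The caps are also assumed: 75, 100 and 150 for 25 of 50; 100 and 150 for 37 of 75.

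**Mechanism.** With n1 participants and statistic z1 at the interim, the chance under no effect that the pooled test favours Active at final size N is

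CE(N) = 1 − Φ[(1.96·√N − z1·√n1) / √(N − n1)].

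For n1 = 25:

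| z1 | N = 50 | N = 100 |
|---|---|---|
| 0 | 1 − Φ(2.772) = 0.28% | 1 − Φ(2.263) = 1.18% |
| 1.0 | 1 − Φ(1.772) = 3.82% | 1 − Φ(1.686) = 4.59% |
| 1.386 | 1 − Φ(1.386) = 8.29% | 1 − Φ(1.463) = 7.17% |

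Differentiating in N shows that CE rises with N while z1 < 1.96·√(n1/N) and falls after that. An increase from the planned N is therefore safe when z1 ≥ 1.96·√(n1/N planned), which is 1.386 for 25 of 50 and 1.377 for 37 of 75. This is the same as conditional power of at least 50% at the planned N under the observed effect, or d ≥ 1.96/√N: 1.96/√50 = 0.28 and 1.96/√75 = 0.23. The expected effects of 0.417 and 0.597 lie above these bounds, so the plan's trigger also covers the region below them, where an increase raises the error.

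**Overall error.** Averaging both tails over the null distribution of z1 returns 5.00% with no adaptation. With an increase:

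| Interim/planned, cap | To cap if d < 0.417 | To cap if d < 0.597 | Re-estimated from signed d (80% power) | Worst increase-only rule |
|---|---|---|---|---|
| 25/50, 75 | 5.22% | 5.03% | 5.30% | 5.79% |
| 25/50, 100 | 5.32% | 5.05% | 5.49% | 6.20% |
| 25/50, 150 | 5.42% | 5.06% | 5.69% | 6.63% |
| 37/75, 100 | 5.07% | 5.00% | 5.22% | 5.58% |
| 37/75, 150 | 5.14% | 5.01% | 5.48% | 6.18% |

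The error in favour of Active (nominal 2.5%) is 2.5-2.9% under the fixed rules and 2.7-3.2% under signed re-estimation. The other tail stays at about 2.5%.

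**Check and remedies.** Simulated paired t-tests (2,000,000 trials per setting) gave 5.00-5.44% for the fixed rules and 5.24-5.73% for signed re-estimation. Limiting increases to z1 at or above the bound gives at most 5.00% for any N up to the cap. The inverse-normal test with stage-wise t-tests gave 4.97-5.03%.

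**The case against.** The strongest reply is that the plan states no rule, so a harmless one may be intended. If N were raised only when the size needed at the observed effect fits under the cap, the level would be 4.89-4.97%. That is correct, but the Interim Analysis section states no such restriction. The accurate claim is that control is not guaranteed, not that it is certainly lost.

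The size also depends on the reading. Half of the enrolled population most naturally means about 37 of 75, where the fixed rules give only 5.00-5.14%. With 75 as a firm ceiling and 50 planned, the range is 5.0-5.3%. An interim at 37 with 50 planned and a cap of 75 gives 5.00-5.16% (fixed) or 5.33% (signed). Back-solving at 90% power instead (d = 0.483 and 0.691) gives 5.00-5.24% for the fixed rules. The 5.7% figure needs 25 of 50, a cap of 150 and signed re-estimation together. All of this stands, and it is why the point is not graded higher. Nor is 6.6% a true ceiling, because the plan names no maximum N.

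It is also fair that a fixed N, with the effect-based trigger dropped, would hold the level without special methods. That remains open to the sponsor, but it gives up the purpose of the interim.

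**Conclusion.** The concern holds. As written, the plan allows an increase triggered by a low observed effect, sets no promising-result limit and no ceiling, and keeps an unadjusted test at 0.05. Under rules that follow its wording the true level is about 5.0-5.7%, with the excess on the Active side. These figures rest on the assumed expected effects, caps and 80% power, and on a single endpoint, channel and test. The inflation is modest, and the point should be fixed because a change of wording settles it before the interim is looked at.

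**What to change.** Amend Interim Analysis and Primary Efficacy Analysis in one of two ways. In both, state the rule for increasing N, the maximum N, and whether it may exceed 75.

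**(a) Keep the trigger and change the final test.** Use Z = √w·z1 + √(1 − w)·z2 and reject if |Z| > 1.96 (inverse-normal, Cui-Hung-Wang). Take z1 and z2 from one-sided p-values of one test chosen in advance (paired t or Wilcoxon), applied separately to participants before and after the interim. Fix w as planned interim completers over planned final completers (25/50 = 0.50; 37/75 = 0.49; 37/50 = 0.74), and leave it unchanged if N rises.

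**(b) Keep the ordinary test and restrict the trigger.** Allow an increase only if conditional power at the planned N, under the observed effect, is at least 50%: observed d of at least 0.28 for N = 50 or 0.23 for N = 75.

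**Cost.** The amendment is wording only, but each option has a price in power.

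- Option (a) loses 0.0-0.4 points if N is unchanged. When N can rise, it loses 0.1-1.1 points at d = 0.42, 0.8-4.0 at d = 0.30 and 0.9-6.3 at d = 0.25, compared with a pooled test that does not hold 5%.
- Option (b) gives up increases after very low interims. At a true d of 0.30 the interim falls below the bound in about 45% of trials (25 of 50) or 33% (37 of 75).
- With 25 of 50, a cap of 75 and an increase if d < 0.417, power at d = 0.30 is 68.7% under (a) (mean N 68) and 59.0% under (b) (mean N 56). Most of that gap is extra participants: a fixed N of 50 gives 54.8% and a fixed N of 75 gives 72.7%.
- Neither option offers a material gain over a fixed design of equal size. At d = 0.30, (a) with re-estimation and a cap of 100 gives 75.1% at mean N 77; a fixed N of 78 gives 74.4%.

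Option (a) keeps the purpose of the interim; option (b) is simpler.
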